### *Sample Size Estimation*

The sample size estimation for the study is based on the association between IR and devices that may have sufficient electromagnetic charge to affect programmable valves. We estimate that the frequency of exposure to the devices in patients with IR is 10 to 30% and on average each patient may be evaluated at least three times. Based on these estimates, we will need 996 participants to have 90% power at the two-sided alpha level of 0.05 to detect an odds ratio of 2.0 assuming an exposure frequency of 10% (most conservative estimate). If the exposure is 30% we will need 399 participants to obtain the same effect estimate (see Table X below).

Table - Sample size required for different frequencies of exposure, alpha=0.05 (two-sided), power=90% and odds ratio=2.0

Frequency of exposure (%)	10	15	20	25	30
Sample size	996	692	542	455	399

A sample size of 996 will allow us to estimate IR frequency (Aim #1) of 5% with a precision of 1.4% (using a 95%CI).

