### *Statistical Considerations*

The statistical analysis will be supervised and performed by [name] and his colleagues at the ACH/JHM CTRO. Demographic and clinical characteristics will be reported by IR status and compared using  $\chi^2$  or Fishers exact tests for categorical measures and t-test or Mann-Whitney U tests for continuous measures.

Aim #1: The frequency of IR will be calculated as the number of hydrocephalic children with Strata CSF shunt valves who had IR divided by the total number of hydrocephalic children with Strata CSF shunt valves.

Aim #2: The association between the field strength of MRI scanning and IR will be determined using unadjusted and adjusted generalized estimating equation models that account for multiple evaluations of participants. IR will be a binary outcome variable (IR present vs IR absent) and the field strength of MRI (3T vs 1.5T) will be the predictor variable. The adjusted model will include potential confounders that will be selected based on prior knowledge of factors established to be associated with IR as well as additional factors with p-value <0.1 in univariate analyses.

Aim #3: We will compare the proportion of patients with signs, symptoms or radiographic changes suggestive of shunt malfunction between the IR and no IR groups using  $\chi^2$  or Fishers exact tests for categorical measures and t-test or Mann-Whitney U tests for continuous measures

Aim #4: The association between devices that may have sufficient electromagnetic charge to affect programmable valves and IR will be determined using unadjusted and

Date: 4/19/2016 V.2  
Principal Investigator: [name]  
Application Number: IRB00093490

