### *Interim Analyses and Possible Early Termination of Study*

There are a number of factors that may lead to early termination of the study, including difficulties estimating the number of encounters per center as well as the true frequency of IR. Each center listed in the study has made estimates of their current Strata valve interrogation rates, but they can vary widely by month. Also, because the true prevalence and the implications of IR are unknown, estimating an adequate sample size to show an association between device exposure and IR is difficult.

We have budgeted for enough encounters to reach the sample size adequate to predict IR with reasonable precision. Our calculations suggest that 996 encounters

Date: 4/19/2016 V.2  
Principal Investigator: [name]  
Application Number: IRB00093490

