## **JHM IRB - eForm A – Protocol**

will be necessary. We budgeted for 1,215 encounters to allow for difficulties we may face related to a multiplicity of encounters per patient, to possible inaccuracies in valve assessment, or due to inevitable human error.

In order to address these difficulties in estimating a necessary sample size, the coordinating center will carefully follow data trends. The study coordinator [name] will work closely with [name] and [name] to report interim results to the ACH study group at least every six months. If strong statistical associations between IR and the other factors being studied can be made with lesser sample sizes, the study will be terminated ahead of schedule and the results will be published promptly.

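### The sample size of 996 is derived in participants but budgeted in encounters; at three encounters per child the 1,215-encounter budget is about 405 children, which undercuts both the power and the Aim 1 precision claims

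*Combined protocol and SAP*

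**What the plan says.** All of this is in section 7, Study Statistics.

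- **Sample Size Estimation** bases the size on the association between device exposure and inadvertent reprogramming (IR), which is Aim 4. It takes exposure of 10 to 30% and assumes that "on average each patient may be evaluated at least three times". From these it concludes that "we will need 996 participants to have 90% power at the two-sided alpha level of 0.05" for an odds ratio of 2.0 at 10% exposure, which it calls the most conservative case. At the other end, "If the exposure is 30% we will need 399 participants". The table gives 996, 692, 542, 455 and 399 at 10, 15, 20, 25 and 30% exposure.
- The same section uses 996 for Aim 1: "A sample size of 996 will allow us to estimate IR frequency (Aim #1) of 5% with a precision of 1.4" percent, on a 95% confidence interval.
- **Statistical Considerations** defines the Aim 1 frequency as children with IR "divided by the total number of hydrocephalic children with Strata CSF shunt valves". The unit is the child.
- **Interim Analyses and Possible Early Termination of Study** says: "We have budgeted for enough encounters to reach the sample size adequate to predict IR with reasonable precision". It continues: "Our calculations suggest that 996 encounters" are needed. Then: "We budgeted for 1,215 encounters to allow for difficulties we may face related to a multiplicity of encounters per patient", with inaccurate valve assessment and human error given as further reasons for the margin.

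**The concern.** One number carries two units. In the sample size section 996 counts children, each seen about three times or more. In the interim section 996 counts visits. Under the plan's own visit assumption these are different studies, and nothing in the plan reconciles them. The plan does admit that its sample size is uncertain, but it attributes this to the unknown IR rate and variable encounter volume, not to a change of unit.

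Two things depend on the answer. First, a null result on household devices could be presented as coming from a study with 90% power when the budgeted study had much less at the exposure level chosen for the headline figure. Second, the unit decides when recruitment is complete. A team counting 996 children and a team counting 996 encounters would stop at very different points.

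**Working it through.** **Inputs from the plan:** 996 participants; at least three evaluations per participant; table entries 996, 692, 542, 455, 399; two-sided alpha 0.05; power 90%; odds ratio 2.0; Aim 1 IR frequency 5%; budget 1,215 encounters.

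**1. The plan's own precision figure.** Half-width = 1.96 × √(p(1 − p)/n). With p = 0.05 and n = 996 this is 1.96 × √(0.0475/996) = 1.35 points, which rounds to the stated 1.4. The figure is right for 996 independent units, and Aim 1 makes those units children.

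**2. The plan's own 996.** It cannot be derived from the stated inputs alone, because the IR rate and the within-child correlation are missing. A log-odds-ratio formula with three evaluations per child comes close under two assumed values, IR 20% and correlation 0.35: it gives 1000, 694, 545, 457 and 402. That solution is not unique. Among the formulas tried with one observation per unit, the table is approached only with an IR rate of about 37 to 40% or more in the unexposed. The table therefore looks more like a count of children seen three times than a count of single encounters.

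**3. Converting the units.**
- Encounters for 996 children: 996 × 3 = 2,988, which is 2,988/1,215 = 2.46 times the budget.
- Children within the budget: 1,215/3 = 405, which is 405/996 = 41% of the stated size.
- Children in 996 encounters: 996/3 = 332.
- Visits per child if 996 children are to fit the budget: 1,215/996 = 1.22.
- Margin in the budget: 1,215 − 996 = 219 encounters, or 22%.

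**4. Power with 405 children.** Required N is proportional to (z for alpha + z for power)², so each table entry can be scaled: power = Φ((1.960 + 1.2816) × √(405/N) − 1.960), where N is the table entry.

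| Exposure | Table N | Encounters at 3 each | Power with 405 children |
|---|---|---|---|
| 10% | 996 | 2,988 | 54% |
| 15% | 692 | 2,076 | 70% |
| 20% | 542 | 1,626 | 80% |
| 25% | 455 | 1,365 | 86% |
| 30% | 399 | 1,197 | 90% |

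Only the 30% column fits within 1,215 encounters. Linear interpolation between 455 and 399 puts the 90% threshold at 25 + 5 × (455 − 405)/(455 − 399) = 29.5% exposure.

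**5. Aim 1 precision at 5% IR.** With 405 children: 1.96 × √(0.0475/405) = 2.12 points. With 332 children: 2.34 points.

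**6. Sensitivity to visits per child, with the budget fixed at 1,215.** Power here also needs an assumed correlation; 0.35 is used. A child seen m times counts as m/(1 + 0.35(m − 1)) independent observations, against 3/1.7 = 1.76 at three visits. The number of children times that ratio gives the equivalent number of three-visit children, which goes into the formula in step 4 with N = 996.

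| Visits per child | Children | Aim 1 half-width | Equivalent three-visit children | Power at 10% exposure |
|---|---|---|---|---|
| 1.22 | 996 | 1.4 | 639 | 74% |
| 2 | 608 | 1.7 | 510 | 64% |
| 3 | 405 | 2.1 | 405 | 54% |
| 4 | 304 | 2.5 | 336 | 47% |

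Under this assumption no row reaches 90% at 10% exposure.

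**The case against.** The strongest reply is that the slip lies in the other place: the table was meant in evaluations, and the word participants is the mistake. Then 1,215 exceeds 996 and Aim 4 is not short of power. This cannot be excluded, because the formula is not given. But the sample size section uses participants twice, and the table fits poorly with one observation per unit (step 2). Nor does this reading rescue Aim 1, which is defined per child: at three visits each, 996 to 1,215 encounters are 332 to 405 children, and the half-width is 2.1 to 2.3 points.

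A second reply is that three visits is only a planning average and that the budget already allows for repeat visits. The margin of 22% covers 1.22 visits per child, not three. If children did average 1.22, the 1.4-point precision would hold, but the three-evaluation input behind 996 would fail. The plan cannot keep both.

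Third, the shortfall should not be overdrawn. From 20% exposure upward power is still 80% or more, and a 2.1-point half-width around 5% remains usable for a descriptive aim. That is fair: the serious loss is at 10 to 15% exposure. However, 10% is the case the plan itself chose for its headline number.

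**Conclusion.** The concern holds. The same 996 appears as participants and as encounters, and the plan's own three-visit assumption makes these at least threefold apart. If the budget stands and children average three encounters, the study has about 405 children, 41% of the number behind its headline claims. Power at an odds ratio of 2.0 is then about 54% at 10% exposure and reaches 90% only near 30%. The Aim 1 half-width is about 2.1 points instead of 1.4.

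The power figures rest on three visits per child and on the unstated IR rate, correlation and formula behind the table. More visits per child would make the shortfall larger and fewer would make it smaller. The precision figure does not depend on exposure. It takes the plan's 5% as a per-child frequency; if 5% were meant per encounter, the share of children ever having IR would be higher and the interval wider.

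**What to change.** Use one unit throughout section 7, and state the IR rate, within-child correlation and formula behind the table. Then choose one of the following.

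- **Keep the 1,215-encounter budget.** Restate the size as about 405 children at three encounters each. Report power for an odds ratio of 2.0 as about 54, 70, 80, 86 and 90% at 10, 15, 20, 25 and 30% exposure, labelled as conditional on three visits per child and the disclosed assumptions. Restate Aim 1 precision as about ±2.1 points at 5% IR. The cost is wording and less favourable figures; no extra patients are needed.
- **Keep 996 participants.** Correct the encounter requirement to at least 2,988 and revise the budget. The cost is at least 2,988 − 1,215 = 1,773 further encounters.
- **If the table was in fact computed in evaluations,** say so and show the calculation, including how repeated visits by the same child were handled. The Aim 1 precision must still be restated for the number of children expected.

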### *Interim Analyses and Possible Early Termination of Study*

There are a number of factors that may lead to early termination of the study, including difficulties estimating the number of encounters per center as well as the true frequency of IR. Each center listed in the study has made estimates of their current Strata valve interrogation rates, but they can vary widely by month. Also, because the true prevalence and the implications of IR are unknown, estimating an adequate sample size to show an association between device exposure and IR is difficult.

We have budgeted for enough encounters to reach the sample size adequate to predict IR with reasonable precision. Our calculations suggest that 996 encounters

Date: 4/19/2016 V.2  
Principal Investigator: [name]  
Application Number: IRB00093490

## **JHM IRB - eForm A – Protocol**

will be necessary. We budgeted for 1,215 encounters to allow for difficulties we may face related to a multiplicity of encounters per patient, to possible inaccuracies in valve assessment, or due to inevitable human error.

In order to address these difficulties in estimating a necessary sample size, the coordinating center will carefully follow data trends. The study coordinator [name] will work closely with [name] and [name] to report interim results to the ACH study group at least every six months. If strong statistical associations between IR and the other factors being studied can be made with lesser sample sizes, the study will be terminated ahead of schedule and the results will be published promptly.

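### The rule to stop and publish on strong associations sets no threshold, trigger, maximum number of looks or boundary, so its error rate is uncontrolled

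*Combined protocol and SAP*

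**What the plan says.** Under Interim Analyses and Possible Early Termination of Study (section 7), study staff will "report interim results to the ACH study group at least every six months". The stopping rule follows: "If strong statistical associations between IR and the other factors being studied can be made with lesser sample sizes", then "the study will be terminated ahead of schedule and the results will be published promptly". The stated motive is uncertainty about sample size: "estimating an adequate sample size to show an association between device exposure and IR is difficult", and "In order to address these difficulties in estimating a necessary sample size, the coordinating center will carefully follow data trends".

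Sample Size Estimation gives the only significance level for testing: "we will need 996 participants to have 90% power at the two-sided alpha level of 0.05", for an odds ratio of 2.0. It makes no allowance for interim looks. The p<0.1 under Statistical Considerations is for selecting confounders.

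The two subsections count in different units. Sample Size Estimation speaks of 996 participants. The interim subsection says "Our calculations suggest that 996 encounters" are needed, and then "We budgeted for 1,215 encounters to allow for difficulties we may face related to a multiplicity of encounters per patient".

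**The concern.** The sentence is an operative rule: if the condition is met, the study ends and the results are published. Four things needed to apply it are missing:

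- the threshold for *strong*;
- the association, or number of associations, that triggers stopping;
- the maximum number of looks (the plan sets only a minimum frequency);
- a stopping boundary or other allowance for repeated testing.

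The candidate triggers are many. Section 2 lists MRI field strength (hypothesis 2a), signs, symptoms and radiographic findings (3a, 3b) and device exposure (4a to 4c), and the exposure table in Background has 12 rows. All are associations with inadvertent reprogramming (IR).

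Without these definitions the choice can be made after the data are seen. At stake is the credibility of the published associations. Background says the results should inform decisions about avoiding household devices and about surgery to replace valves. Aim 1, the IR frequency, would also be estimated from a smaller sample because of a trigger unrelated to it.

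**Working it through.** **Inputs from the protocol.** Two-sided alpha 0.05, 90% power, odds ratio (OR) 2.0, N = 996, at least three evaluations per patient on average, and Aim 1 precision of 1.4% at 5% IR (Sample Size Estimation); reports at least every six months (interim subsection); three-year enrollment (section 4, Participants).

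**Assumptions.** Equally spaced looks, normal test statistics, interim threshold p<0.05, 0.01 or 0.001, and a final test at 0.05. Six-monthly looks over three years give 36/6 = 6. Twelve is shown because no maximum is set and section 7 says the duration may change.

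**1. The plan's own precision figure.** Half-width = 1.96 × √(0.05 × 0.95 / N).
- N = 996: 0.0135, or 1.4%, as stated.
- N = 498 (half): 0.0191, or 1.9%.

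Both treat N as independent children. The figure 996 itself cannot be re-derived, because its calculation states neither a baseline IR rate nor a within-patient correlation. Nothing below depends on it.

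**2. Error rate for one factor with no true association.** With K looks, information at look k is t = k/K and z = B(t)/√t, where B is Brownian motion. A false positive is |z| above the interim threshold at any look before the last, or above 1.96 at the last. Simulated with at least 1,000,000 replicates per cell:

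| Meaning of *strong* | 6 looks | 12 looks |
|---|---|---|
| p<0.05 | 15.5% | 20.7% |
| p<0.01 | 6.8% | 8.0% |
| p<0.001 | 5.1% | 5.2% |

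The excess over 5% is about 0.1 to 10.5 points at six looks and 0.2 to 15.7 points at twelve.

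**3. Bias in the odds ratio.** For 90% power at full information the drift at OR 2.0 is 1.960 + 1.282 = 3.2415. The estimate at information t is ln OR = ln 2 × z / (√t × 3.2415). At half information (√t = 0.7071), the smallest OR that can trigger a stop is:
- p<0.05: exp(0.693 × 1.960 / 2.292) = 1.81
- p<0.01: exp(0.693 × 2.576 / 2.292) = 2.18
- p<0.001: exp(0.693 × 3.291 / 2.292) = 2.70

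A stricter threshold admits only larger estimates. Simulated with six looks and true OR 2.0:

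| Interim threshold | Runs stopping early | Median OR if stopped early | Median OR, all runs |
|---|---|---|---|
| p<0.05 | 88% | 2.34 | 2.22 |
| p<0.01 | 70% | 2.47 | 2.19 |
| p<0.001 | 41% | 2.72 | 2.07 |

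With a fixed sample the median is 2.00.

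**4. Unit of information.** At three evaluations per child, 996 participants mean 996 × 3 = 2,988 encounters, of which the 1,215 budgeted are 41%. Read as encounters, 996 means 996/3 = 332 children. The information fraction at a look cannot be stated until one unit is chosen.

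**5. A boundary that controls error.** For six equal looks, an O'Brien-Fleming-type spending boundary is z = 4.80, 3.40, 2.79, 2.45, 2.23, 2.08 (nominal p about 0.000002, 0.0007, 0.005, 0.014, 0.026, 0.038). Simulated null error is 5.0%. Power at OR 2.0 is 89%, with 78% of runs stopping before the last look.

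**The case against.** The strongest defence is that *strong* may mean a strict threshold, that the sentence speaks of associations and factors in the plural, and that the study is observational, with no treatment arm and no declared primary hypothesis. Much of this stands. At p<0.001 the one-factor excess is negligible, and if several associations had to cross together, a false early stop would be rare: 2.8% at p<0.05 when two of three independent null factors must cross at the same look. The harm is to published results, not to participants.

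A reader might infer that the rule makes a false finding likely. If any one of three independent null factors could stop the study at p<0.05, overall error over six looks would be 40%. The documents do not support that inference: they state neither this trigger, nor this threshold, nor three factors. Three tests at a single look already give 1 − 0.95³ = 14.3%, so even there the rule adds only about 25 points, and at p<0.001 about 0.4.

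The defence does not remove the defect. Nothing commits the sponsor to the strict reading, and a strict threshold makes the bias in early-stopped runs larger. The participant-encounter mismatch would remain if the stopping sentence were deleted. It matters here because any boundary needs an information fraction.

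**Conclusion.** The point holds: the error rate of the stopping rule is uncontrolled, not shown to be large. For one factor it lies between 5.1% and 15.5% at six looks and between 5.2% and 20.7% at twelve, depending on the meaning of *strong*. It is higher if any one of several factors may trigger stopping. At a true OR of 2.0, early-stopped runs report a median of about 2.3 to 2.7; over all runs the bias is modest. Stopping at half of 996 independent children moves the Aim 1 half-width from 1.4% to 1.9%.

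These sizes rest on the assumed looks, thresholds and 90% power at full information. The absence of a threshold, trigger, maximum number of looks and boundary rests on the text alone. This should be fixed, but it does not invalidate the study.

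**What to change.** Adopt one of two changes, each about a paragraph of protocol text.

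**Option 1: descriptive reports only.** Replace the stopping sentence with, for example: *Six-monthly reports will give the number of encounters, the number of children, overall IR frequency and overall exposure frequency. No association with IR will be tested before enrollment ends.* This informs the sample-size uncertainty that motivates the rule but does not resolve it, since no rule links those frequencies to a sample-size decision. It gives up early publication.

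**Option 2: stopping on one test only.** Specify:
- one pre-defined exposure variable (for example, any listed device, yes or no) in one named model. Naming hypothesis 4a is not enough, because it covers several items and Aim 4 plans unadjusted and adjusted models. A 5% boundary applied separately to three independent devices gives about 14% error;
- a fixed number of looks;
- information counted in children or in encounters, with the two subsections reconciled;
- an O'Brien-Fleming-type spending boundary at overall two-sided 0.05 (step 5 gives values for six equal looks);
- that no other association may stop the study;
- that the report will say estimates after early stopping are biased away from the null on average.

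At the same maximum sample, Option 2 lowers power at OR 2.0 from 90% to about 89%. It reduces the bias without removing it: the median OR is still about 2.3 in early-stopped runs and 2.07 over all runs.

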### **8) Risks**

There is a slight risk of loss of confidentiality of the participants' information. Every effort will be used to minimize this risk. Protected health information will be removed prior to data entry with the exception of date of service. Data will be stored on a secure server, and hard data will be stored in locked cabinets.

